2.2.3 Types of First Aid Training programs for children

In a bid to develop an Evidence-based Educational Pathway for the integration of FA straining in school curricula, Buck et al. perused studies in the Cochrane Library, Embase and Medline to identify various F A trainings and pathways given to kids. The

studies found included FA training on [14]:

1. Emergency call – which involved calling an emergency number. A recall amongst children 5-16 years old in varying groups and different studies (5-6, 6-7, 10-12, 11-12,13-16, 11-16 years). Also, the “Do Something” intervention which spanned between calling for help and injury FA was a 6-month course taught among 13-to-14-year-olds using a textbook style covering the preparation for action, situational overview, the ABC plan (Airway, Breathing, Circulation), administering FA, and concluding FA. It also included a series of seven (7) videos addressing topics such as chest pain/cardiac arrest, severe epileptic seizure, head or neck injuries, burns, internal bleeding, airway obstruction, and drowning [14].
2. Cardiopulmonary resuscitation (CPR) – hands-on and practised-based use of manikins and simulation to demonstrate scenarios among 6-7-, 11-12-, and 13–16-year-olds [14].
3. AED (Automated External Defibrillator) used among 13 to 19-year-olds via video clips with different cardiac arrest situations [14].
4. Recovery position – this measured the knowledge and ability of children to perform correct recovery position in various studies of children aged 6-7, 10-12, 10-11, 11-12 years old [14].
5. Choking – training children on FA for choking and obtaining their knowledge scores before and after the training or using a control group of “no training” amongst 10-12- and 11–16-year-olds [14].
6. Injuries e.g., an Injury Minimization Program for Schools (IMPS) where a program developed during an entire academic year within the school curriculum for 10- to 11-year-olds. This one contained 2 major packs: an educational pack where kids were

provided with materials and knowledge to handle aspects ranging from road safety, home, fire, electricity accidents, poisons and waterways. The second pack was the hospital visit where children learnt to perform basic life support and resuscitation, watched interactive videos about common accidents (burns, cuts, electrocution, FA responses) and toured the emergency and Accident (E&A) unit [14]. Another example is the “Stop the Bleed” program in the United States that is currently ongoing [17].

7. Poisoning – taught within the FA and home safety training by the American Red cross alongside bites, stings and allergies to 11 to 16-year-olds [46].

Most of these studies measured outcomes in children immediately and sometime after the training (3 to 12 months or thereabouts). However, none of these studies had a qualitative component that evaluated the usability and acceptance of the program. In our context in Cameroon, this is a critical component, particularly with the crises on the NOSO and the increasing educational standards and emancipation of individuals.

Following this study in 2020, an educational pathway was developed outlining the age range for which various FA activities should either be “Encouraged”, “Known or Know How” and/or “Repeated” with specifics as to the knowledge, skills and attitudes regarding the specific act. For instance, preschoolers (3-6 years) should be encouraged to know why they must seek help quickly, should know how to wash their hands, be encouraged to stay safe and to be encouraged to correctly stop nose bleeds. This is different from what is required for 9-10, 11-12, or teenagers of varying age groups where they are required to know and apply certain skills and repeat training is always a bonus. According to this pathway, children should be able to know why and how to call for help in the face of an emergency, put on disposable gloves, ensure their safety, recognize a skin wound, equipment needed for treating a skin wound, correctly treat a

skin wound, correctly apply spiral bandage, correctly stop a nose bleed between 7 and 8 years of age and be encouraged to understand other basic skills. By 9-10 years, they should know that they are not to move seriously painful or hurt parts of the body, know the importance of stopping bleeding as fast as possible, know when to refer a victim with a nosebleed, etc. By 11-12 years, they should receive a repeat of what they know and start applying what they were encouraged to know at a younger age e.g., apply a compression bandage, know 3 possible injuries to the motor system (sprain, dislocation, breakage or fracture), know how to recognize an injury to bones, muscles, or joints. By a later age (13 to 14 years), they should be apt to correctly treat a skin wound if there is no clean water or too little. Correctly treat a wound that contains a foreign object. Correctly remove a splinter. Using disinfectant, know when to refer someone with a splinter to the doctor, among others. As the age group increases, what the child needs is mainly a repeat of what they are expected to know or what they were encouraged to know at an earlier age.

E: Encourage K: Know/Know How R: Repeat	Pre-school (3-6 years)	First grade PS (7-8 years)	Second grade PS (9-10 years)	Third grade PS (11-12 years)	First grade SS (13-14 years)	Second grade SS (15-16 years)	Third grade SS (17-18 years)
1. General Knowledge							
The pupils:							
• Know why they must find help as quickly as possible from an adult in an emergency situation	E	K	R	R			
• Know the general emergency number		K	R	R	R		
• Know the six basic principles of first aid			K	R			
• Know what each emergency service does		E	K	R			
Skills							
The pupils can:							
• Wash their hands	K	R	R	R	R	R	R
• Put on disposable gloves		K		K			
• Use the six basic first aid principles when looking after a victim			E	R	R	R	R
• Recognize the emergency services symbols				K			
Attitudes							
The pupils are prepared:							
• To help	E	K	R	R	R	R	R
• To comfort the victim	E	K	R	R	R	R	R
• To ensure their own safety	E	K	R	R	R	R	R
• To fetch an adult	E	K	R	R	R	R	R
The pupils recognize the importance of:							
• Fetching an adult	E	K	R	R			
• Alerting the emergency services		E	K	R			
• The pupils are prepared to touch a person unknown to them	E		R	R	R		
The pupils recognize the importance of:							
• Avoiding infection				K	R	R	R
• Making the victim comfortable				E	K	R	R
5. Skin wound							
Knowledge							
The pupils:							
• Recognize a skin wound	E	K	R	R			
• Know which equipment is needed for treating a skin wound	E	K	R	R			
• Know when a skin wound is serious and when to refer the victim to the doctor			K	R	R		
• Recognize a graze, a cut and a stab wound		E	K	R	R		
• Know the importance of vaccinations		E	K	R	R		
• Know why tetanus is dangerous and be aware of the link with skin wounds			K	R	R		
• Know that a victim with a foreign body in the wound must always be referred to the doctor			E	K	R	R	

Skills						
The pupils can:						
• Correctly treat a skin wound when water is available	E	K	R	R	R	
• Correctly apply a spiral bandage [technique]		K	R	R	R	
• Stem the bleeding of a wound that does not stop bleeding by itself	E	K	R	R		
• Correctly treat a skin wound if there is no clean water or too little		E	E	K	R	R
• Correctly treat a wound that contains a foreign object				K	R	R
• Correctly remove a splinter				K	R	R
Attitudes						
See Attitudes general learning trajectory						
The pupils recognize the importance of:						
• Using disinfectant (if there is no clean water or too little available)			E	K	R	R
• Correctly treating a wound containing a foreign object			E	K	R	R
6. Burns						
Knowledge						
The pupils:						
• Recognize a burn	E	K	R	R	R	
• Know what to do in the event of a burn (regardless of the degree of the burn)	E	K	R	R	R	
• Know when a burn is serious and when to refer the victim to a doctor	E	K	R	R		
• Know the difference between a first, second and third degree burn			E	K	R	R
• Know that they must alert the emergency services if the burn is serious			E	K	R	R
• Know what can cause a burn (heat, chemicals, ...)	E	E	E	K	R	R
Skills						
The pupils can:						
• Correctly treat a burn	E	K	R	R	R	
• Alert the emergency services if the burn is serious			E	K	R	R
Attitudes						
See Attitudes general learning trajectory						
The pupils recognize the importance of continuously applying water to a burn	E	K	R	R		
• Recognize an injury to bones, muscles or joints			E	K	R	R
• Know the difference between an open and closed injury				K	R	R
Skills						
The pupils can:						
• Correctly treat a minor injury to bones, muscles or joints			E	K	R	R
• Correctly apply a cross-bandage to a hand or foot [technique]			E	K	R	R
• Administer first aid to a victim with an open break				K	R	R
Attitudes						
See Attitudes general learning trajectory						

Figure 2: Table of what children should be Encouraged, Know/Know-How, and when to receive Refresher/Repeat courses on the Previous FA skills.

In the case of injury/trauma it was seen that children 11 to 12 years should Recognize the AED pictogram • Know that they must always call the emergency services if the victim is unconscious (and when the AED box alarm goes off) • Know the purpose of an AED.

However, in Sub-Saharan Africa, there is no FA training in the tender ages. Starting this will require an adaptation of our context to determine when to introduce what and we also need to consider the mindsets of stakeholders.

CHAPTER THREE

MATERIALS AND METHODOLOGY

3.1 STUDY AREA

We will carry out this project in the Fako division of the Southwest Region of Cameroon. The division is made up of four health districts. These are Buea, Limbe, Tiko and Muyuka health districts (HDs). The Buea and Tiko Health Districts will be selected based on the district with the highest number of trauma cases recorded in the DHIS2 and the security situation within the region.

[figure not shown]
[figure not shown]

Figure 3: Map of the Southwest Region of Cameroon. Source, Southwest Regional Delegation of Public Health (RDPH), Cameroon

Source: DHIS2, Minsante, Cameroon

Figure 4: The number of trauma cases recorded in Fako division over 4 years [47]

Although the picture shows a drop in the number of cases recorded over the years, there is a probability that it is mostly due to underreporting of cases as there have been a lot more accidents that have occurred over the years and whose information was not captured by the health districts.

Table 1: Average number of Trauma cases in the past four years on DHIS2 [47]

Source: DHIS2, Minsante, Cameroon

Year	Limbe	Buea	Muyuka	Tiko
2020	614	358	71	1487
2021	694	726	89	1487
2022	372	482	1254	1084
2023	297	385	84	1064
Average	494.25	487.75	374.5	1280.5

Although Limbe is the next district with the next highest number of trauma and injury cases after Tiko, we took Buea to avoid the confounding effects of the Lay First-responders (LFR) program taking place in the Limbe Health District.

3.2 STUDY POPULATION

The qualitative part will include teachers, principals and vice (of the selected schools), parents (whose kids attend the selected schools), regional delegates (of secondary education and public health) and a few community leaders like quarter heads and or chiefs of both the control and the intervention districts of Buea and Tiko.

The cross-sectional survey will involve students in the early secondary school classes (forms 1 to 3) of the selected state secondary schools (SSS) in Buea and Tiko. These classes are chosen because they have most of the children aged 10-14 years which is the age trained in most studies and we believe these ones have just crossed a milestone from the primary school to get to secondary.

The intervention part will also involve the early SSC who take part in the cross-sectional survey before and after the intervention.

The evaluation will involve all the students as well as the stakeholders in both intervention groups who had been interviewed at the start of the study to determine the impact of the YoFA training program and challenges faced. It will also include the students to assess the need for refresher courses on FA for LTB and equally identify challenges faced during the three months prior to the summative evaluation period.

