Buea	1-BGS Molyko	Parents (1) Teachers (1) Students (1)	3
	2-GTHS Molyko	Parents (1) Teachers (1) Students (1)	3
Tiko	1-GHS Mutengene	Parents (1) Teachers (1) Students (1)	3
	2-GTHS Ombe	Parents (1) Teachers (1) Students (1)	3
	Total		12

N.B: Each focused group discussion will be comprised of 5 to 8

Table 3: Number of Participants to be chosen per school for the In-depth interviews

Health District	Schools	Category of Participant	Number per school
Buea	3- GHS Bokwango	Parents (2) Teachers (2) School Admin (1) Students (2)	7
	4-GHS Buea Town	Parents (2) Teachers (2) School Admin (1) Students (2)	7
Tiko	1-GHS Mutengene	Parents (2) Teachers (2) School Admin (1) Students (2)	7
	3-GHS Motombolombo	Parents (2) Teachers (2) School Admin (1) Students (2)	7
	Total		28

B) For the Quantitative or intervention phase

To recruit participants and avoid spill over among initially recruited participants, it was more feasible to randomly choose one classroom from among the selected schools from which to train the students. Thus, instead of table 4 below, we will apply table 5.

Table 4: Initial plan of the YoFA training Participants.

Buea	N	Tiko	N
GHS Bokwango	15	GHS Mutengene	15
GHS Bueatown	15	GTHS Ombe	15
BGS Molyko	20	GBHS Tiko	20
GTHS Molyko	20	GHS Motombolombo	20
TOTAL			70

Table 5: Number of students to train on YoFA Program

Intervention group	School Name	Control	School Name
Buea	BGS Molyko	Tiko	GHS Mutengene
Number of Participants	70		70

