3.11 DATA ANALYSIS PLAN

A difference-in-difference analysis would be done to assess the change in KAPs before and after the intervention in. The posttest would be done immediately after the 4 days of training for each pool and 3 months after the training to assess the need for refresher course planning.

The exposure variables include training on LTBs from injury first aid and the use of these services by the trained students (e.g., the number of persons assisted or referred during the follow-up period of the training).

We will analyze survey data using R Software with a combination of descriptive statistics and parametric and non-parametric tests to establish statistically significant differences between pre- and post-test results and between the intervention and control groups.

Table 7: Objectives and their Indicators

Objective	Activities/process	Data collection tools	Data Source	Indicators
1. To understand the perspectives of stakeholders on YoFA training program among SSC	- In-depth interviews	-In-depth interview guides	School teachers, administrators, parents, community leaders and students	
2. To assess school children's KAP (willingness and self-efficacy on trauma/injury FA via the built YoFA training to stop LTBs.	- survey	-Questionnaire	- students	- Obtain baseline KAP Scores
3. To evaluate the effectiveness and usability of the YoFA training program for SSC to respond to LTBs safely and promptly in their environs.	-Training following a specific STB and LFRs program -Training students on specific modules of LTB FA - Pre and post test -Simulation exercises	- Use adapted tools from the SBEAT - Questionnaires - Evaluation form with questions how? What was the situation?where, and how?	Stakeholders, teachers, parents, students	- Change in knowledge scores -At least 50% of stakeholders rate the program as good/ expectations met - 70% of students rate the program as good/expectations met - Number of children who made use of the FA skills taught
4. To determine the barriers associated with implementing the YoFA program among early SSC in the Fako Division.	- Interviews - Survey	-Interview guides - Questionnaires	- Stakeholders, - Teachers, students	- Perceived reasons and challenges that hinder FA training in schools.

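### The 50% stakeholder-approval indicator for objective 3 would be drawn mostly from adults at schools where the programme was not delivered: only 17–19% of the listed school adults are at the trained school.

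*Protocol*

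**What the plan says.** Section 3.2 of the protocol describes who takes part in the evaluation. Besides the students, it names the stakeholders "as well as the stakeholders in both intervention groups who had been interviewed at the start of the study", and gives the purpose as judging the programme's impact and the challenges met. Section 3.6, Step 3, places this at about the three-month assessment and uses evaluation forms.

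Table 7 in section 3.11 lists four indicators for objective 3 (effectiveness and usability). One of them is "At least 50% of stakeholders rate the program as good/ expectations met". Table 7 does not say which stakeholders give the rating.

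Section 3.5 fixes the people interviewed at the start:

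- Table 2 places focus groups at BGS Molyko, GTHS Molyko, GHS Mutengene and GTHS Ombe, with one parent, one teacher and one student group per school.
- Table 3 places in-depth interviews at GHS Mutengene and GHS Motombolombo in Tiko. In Buea they are at the schools listed as "3- GHS Bokwango" and "4-GHS Buea Town".

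The same section then changes the training plan: "Thus, instead of table 4 below, we will apply table 5". Table 5 names BGS Molyko as the only trained school and GHS Mutengene as the control, and Table 6 agrees. Tables 2 and 3 were left as they stood. Section 3.12 offers training at the other schools only after the study.

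**The concern.** An approval rating can speak to effectiveness or usability only if the raters could have seen the programme or its trained pupils. Here the rating is sought from people chosen to give prior views across several schools and both districts, while training is confined to one school. Section 3.2 refers to two intervention groups, although there is one intervention and one control school, and most of the interviewed adults belong to schools that are now in neither.

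At stake is what the 50% mark can mean. A pass could be produced largely by adults who like the idea of first aid training but never saw it, and a fail by adults with no basis for a favourable rating. The adult part of the closing report on challenges has the same weakness: most of those adults are not where the difficulties would arise.

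**Working it through.** **Inputs.** All come from section 3.5: two adult focus groups (parents, teachers) at each of four schools; 5 to 8 per group, read as participants; five adults (two parents, two teachers, one administrator) and two students in in-depth interviews at each of four schools.

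**The plan's own totals.** Focus groups: 4 × 3 = 12, as in Table 2. In-depth interviews: 4 × (2 + 2 + 1 + 2) = 28, as in Table 3. Both are reproduced.

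**School-based adults.**

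- Focus groups: 4 × 2 × 5 to 8 = 40 to 64, of whom BGS Molyko has 2 × 5 to 8 = 10 to 16.
- In-depth interviews: 4 × 5 = 20, of whom BGS Molyko has 0. All four administrators are in this set.
- Total: 60 to 84. Untrained schools: 60 − 10 = 50 to 84 − 16 = 68.

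**Share at the trained school.** 10/60 = 17%; 16/84 = 19%.

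**Other readings of who rates.**

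| Reading | At BGS Molyko | Share |
|---|---|---|
| All listed adults, equal group sizes | 10/60 to 16/84 | 17–19% |
| All listed adults, smallest groups at BGS and largest elsewhere, or the reverse | 10/78 to 16/66 | 13–24% |
| Interviewed students counted as stakeholders too | 15/88 to 24/124 | 17–19% |
| Buea adults only | 10/30 to 16/42 | 33–38% |
| Only the two schools of Table 5 (Mutengene: 10–16 in groups + 5 interviews) | 10/25 to 16/37 | 40–43% |
| In-depth interviewees only, adults | 0/20 | 0% |

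Adults at the trained school are a minority in every row.

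**Schools in neither arm after Table 5.** GTHS Molyko and GTHS Ombe give 20 to 32 focus group adults; Bokwango, Buea Town and Motombolombo give 15 interviewees. That is 35 of 60 to 47 of 84, or 58% to 56%.

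**What the indicator can reach.**

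- If only BGS Molyko adults approve, the maximum is 10/60 to 16/84 = 17–19%, and the mark is missed.
- If all BGS Molyko adults approve, the share still needed from untrained schools is (0.5 × 60 − 10)/50 = 40%, or (0.5 × 84 − 16)/68 = 38%.

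**Effect of moving training to one school.** Under Table 4, all four Buea schools would have been trained: 20 to 32 focus group adults + 10 interviewees = 30 of 60 to 42 of 84, or 50%. Table 5 cuts this to 17–19%.

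**Unlisted stakeholders.** Section 3.2 adds regional delegates and "a few community leaders like quarter heads and or chiefs", without numbers. To end the majority from untrained schools, even if all of them counted as having seen the programme, 50 − 10 = 40 to 68 − 16 = 52 would be needed.

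**Challenges.** Students report these too: section 3.2 says "It will also include the students to assess the need for refresher courses on FA for LTB and equally identify challenges faced". With 140 students (Table 5) or 145 (Table 6) added, adults at untrained schools are between 50/(60 + 145) = 24% and 68/(84 + 140) = 30% of respondents.

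**The case against.** The strongest reply is that the denominator is inferred. Table 7 does not identify the raters and gives a broad list of data sources. Section 3.6 speaks of evaluation forms without tying them to the people in Tables 2 and 3, section 1.1.2 adds feedback forms from community members, and an analysis plan not shown here might define the set. This stands as a caution. But section 3.2 is the only place that says who returns to judge impact, and it points to those interviewed at the start. No other stakeholder sample is defined.

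It can also be said that the indicator is minor: one of four for objective 3, descriptive and untested. The knowledge, attitude and practice result rests on the students' difference-in-differences analysis, and usability also on the adapted usability scale. That stands and limits the weight of the point. Adults elsewhere can also fairly answer the section 3.6 question about adding first aid to curricula, and the wide sample suits objective 1. The defect is only in using that sample to rate the programme.

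Four stronger readings are tempting and are not supported:

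- A reader might infer that the report on challenges comes mostly from these adults. It does not: students report too, and section 3.6 plans school visits every two weeks to record experiences and challenges.
- A reader might infer that no administrator of BGS Molyko will be asked. Table 3 allocates none, but section 3.2 includes principals of the selected schools, and section 3.6 plans interviews with principals without naming schools.
- A reader might blame the change from Table 4 to Table 5 alone. Section 3.2 includes control stakeholders in any case, so half the adults would have been at untrained schools under Table 4. Nor does the protocol say that Tables 2 and 3 were drawn to match Table 4; GBHS Tiko is in Table 4 but in neither of the others.
- A reader might set the 33–38% Buea share against the 50% threshold. One is a share of respondents and the other a share of favourable ratings, so the comparison means nothing.

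**Conclusion.** The point holds for the stakeholder rating and for the adult part of the report on challenges. As written, about four-fifths of the listed school adults behind the 50% indicator (81–83%) are at schools where the programme was not delivered, so the indicator mainly measures opinion there. The move to one school cut the trained-school share from about 50% to 17–19% but is not the sole cause.

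This rests on three assumptions: focus groups of 5 to 8 people; delegates and community leaders left out for want of numbers; and the raters of Table 7 being the stakeholders of section 3.2. It also counts every BGS Molyko adult as able to judge, which is generous, since section 3.2 asks only that parents have a child at a selected school, not a trained child.

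The student outcomes, student reports and fortnightly visits are untouched. The indicator should be corrected before it is used as evidence on objective 3, but the main comparison does not depend on it.

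**What to change.** In section 3.2 and Table 7, define the 50% indicator on parents, teachers and administrators of BGS Molyko only. Report the ratings of adults at other schools separately, as views on acceptability. Correct the reference to two intervention groups in section 3.2 at the same time.

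Leave the baseline interviews and focus groups of Tables 2 and 3 unchanged, because objective 1 needs their spread. Moving the Buea baseline interviews to BGS Molyko would damage it. Instead, hold closing interviews at BGS Molyko, including one with an administrator, in place of some at untrained schools.

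The cost is a few edits and no additional interviews. There are two downsides. The denominator is small: with 10 to 16 focus group adults, one person moves the indicator by 1/10 to 1/16, or about 10 to 6 percentage points. Five closing interviews on the Table 3 pattern would raise it to 15 to 21. And some closing respondents would have no baseline interview, so their views could not be compared over time.
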